## **10.0 CORRELATIVES/SPECIAL STUDIES**

The goal of the planned laboratory correlative studies is to improve our understanding of the biological processes that drive GVHD and its clinical outcomes.

### **10.1 Sample Collection Guidelines**

The correlative sample collection schedule is detailed in section 6.3 above. Serum will be collected in no additive, silicone coated glass or plastic tubes containing no anticoagulant (red or gold top tube). Samples will be processed at the participating center and batch shipped to [name] Laboratory quarterly for storage. Sample processing details are found in Appendix A. Instructions for quarterly batch shipping are found in the MAGIC Sample Collection and Storage Manual.

### **10.2 Assay Methodology**

See Appendix A.

### **10.3 Specimen Banking**

Patient samples collected for this study will be stored indefinitely or until they are used up. If future use is denied or withdrawn by the patient, best efforts will be made to stop any additional studies and to destroy the specimens. In addition to the biomarker studies planned as part of this study, additional studies may be performed on the banked research samples as part of collaborations with other institutions and entities.

The specimens, DNA, and their derivatives may have significant therapeutic or commercial value. The Informed Consent form contains this information and informs the subject that there is the potential for financial gain by the Icahn School of Medicine at Mount Sinai, the investigator or a collaborating researcher or entity.

The following information obtained from the subject's medical record may be provided to research collaborators when specimens are made available:

- Diagnosis
- Collection time in relation to study treatment
- Clinical outcome – if available
- Demographic data

## 11.0 STATISTICAL CONSIDERATIONS

### 11.1 Study Design/Study Endpoints

This is a proof of concept pilot single arm, open label multicenter clinical trial. The primary study measure of efficacy is the incidence of steroid-refractory GVHD by Day 100 after HCT. GVHD is defined as steroid refractory if CR or PR is not achieved by day 28 of systemic steroid treatment **OR** if additional immunosuppression beyond steroids was given for treatment of GVHD prior to 28 days of steroid treatment. Subjects who start treatment for GVHD within 28 days of Day 100 (i.e., on or after Day 72 post-HCT) must be followed for a full 28 days of systemic steroid treatment for the purposes of assessing the primary study measure of efficacy.

Because we expect improvements in the incidence of steroid refractory GVHD to translate into better long-term outcomes, secondary endpoints include 6 month NRM and 6 months overall survival. Additional secondary endpoints related to efficacy will include, in subjects who develop GVHD, time to discontinuation of steroid therapy, number of lines of GVHD therapy, and cumulative incidence of chronic GVHD. Secondary endpoints related to safety include 6 month and 1 year relapse rates and incidence of serious (BMT CTN grade 3) infections by day 100.

The historical control population for this study consists of patients who met the criteria for a high MAGIC GVHD risk score at either day 7 and 14 (see Background).

### 11.2 Sample Size and Accrual

This is a proof of concept pilot study intended to determine if sufficient evidence can be developed to warrant further study of pre-emptive treatment with AAT. The expected incidence of steroid refractory GVHD by day 100 in patients who are high risk at either day 7 or 14 is 28%. We assume that the incidence of steroid refractory GVHD by day 100 among high risk patients treated pre-emptively will be 15% as a clinically meaningful incidence. Based on this assumption, a sample size of 30 achieves 85% power to detect a 13% improvement (28%-15%) in steroid refractory incidence rate using a one-sided exact test with a target significance level of 0.23. It is suggested in the literature that in pilot studies, false positive rates up to 0.25 could be used as those studies are not designed to provide definite evidence but are designed to provide guidance to whether a larger study should be conducted. If we observe 6 or fewer cases of SR GVHD, we will consider this approach sufficiently promising to warrant further study.

Sample size calculations were computed using the binomial enumeration of all possible outcomes method in PASS 14 Power Analysis and Sample Size Software (2015) NCSS, LLC. Kaysville, Utah, USA, [ncss.com/software/pass](http://ncss.com/software/pass).

The five centers participating in this clinical trial collectively perform >600 allogeneic HCT per year, of whom >90% should meet the eligibility criteria for this trial. We will need to screen approximately 120 eligible patients in order to enroll 30 high risk patients onto this clinical trial. We expect to be able to meet our accrual goals within one year.

### 11.3 Data Analyses Plans

The primary endpoint is incidence of steroid-refractory GVHD by day 100. Death, lack of GVHD response to systemic steroids by day 28 of treatment, or initiation of additional systemic immunosuppressive therapy for GVHD will be considered failures for this

endpoint. The incidence of steroid-refractory GVHD by day 100 in the study patients will be compared to the historical control rate of 28%.

Secondary outcomes such as the overall response rate (CR+PR), the incidence of severe GI GVHD (stage 3 or 4), non-relapse mortality, relapse rates, overall survival, will be estimated and compared to historical controls.

Continuous variables will be summarized using standard summary statistics such as number of observations (n), mean, standard deviation (SD), minimum and maximum values, median, and 1st and 3rd quartiles. Categorical variables will be summarized in frequency tables as counts and percentages.

Cumulative incidence of non-relapse mortality will be estimated by Gray's method and relapse will be considered as a competing risk. Disease free and overall survival, defined as the time from the transplantation to death or to last follow-up if alive, will be estimated by the method of Kaplan-Meier and the probability curves and 95% confidence intervals will be provided based on the method of Brookmeyer and Crowley.

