Several pre-HCT clinical risk factors predict a higher risk of NRM, such as HLA mismatch, non-family member donors, age of the recipient, and the intensity of the conditioning regimen. Importantly, the MAGIC algorithm also stratified patients into distinct risk groups independently of patient age [ $\leq 21$  y: HR 27% vs LR 6%,  $p<0.001$ ;  $> 21$  y: HR 29% vs LR 8%,  $p<0.001$ ], conditioning regimen [reduced intensity: HR 37% vs LR 8%,  $p<0.001$ ; full intensity: HR 25% vs LR 8%,  $p<0.001$ ] or the use of thymoglobulin in the conditioning regimen [ATG given: HR 31% vs LR 8%,  $p<0.001$ ;

no ATG: HR 28% vs LR 8%,  $p<0.001$ ]. Relapse rates were equivalent within all subgroups of clinical risk factors, resulting in a decrease of at least 20% in overall survival for HR patients

We recently tested whether we could improve the sensitivity of the MAGIC algorithm by re-testing low risk patients one week later (Day 14), reasoning that the concentration of GVHD biomarkers would be higher one week closer to the onset of GVHD. Serum samples from both Day 7 and Day 14 were available for 768 MAGIC patients (Figure 2) We measured ST2 and REG3 $\alpha$  on Day 7 in all patients and identified 145 (19%) as high risk and 623 (81%) as low risk with distinctly different NRM (26% vs 8%,  $p<0.001$ ). Twenty low risk patients (3%) developed GVHD between Day 7 and Day 14 and were excluded from further analysis. When we repeated the test on Day 14 in the remaining 603 LR patients, we identified 60 additional HR patients whose NRM risk was similar to the day 7 HR patients and significantly higher than the 543 patients who remained LR (24% vs 6%,  $p<0.001$ ). Compared to the Day 7 test alone, repeat testing on Day 14 resulted in a large improvement in sensitivity for NRM (46% to 61%) with only a modest loss of specificity (80% to

75%). Serial testing at both Days 7 and 14 significantly increases the proportion of patients potentially eligible to participate in a GVHD pre-emptive treatment trial from 19% (145/768) of the total population to 27% (205/768).

For this proof of concept pilot trial we will use the incidence of SR GVHD by day 100 as the primary endpoint to determine whether pre-emption therapy with AAT warrants further study. **The cumulative incidence of SR GVHD by day 100 in patients who are HR at either Day 7 or 14 is 28%.**

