### **2.3 Primary Endpoint**

1. Proportion of HR patients who develop steroid refractory GVHD by day 100 post HCT.

GVHD is defined as steroid refractory if CR or PR is not achieved by day 28 of systemic steroid treatment **OR** if additional immunosuppression beyond steroids was given for treatment of GVHD prior to 28 days of steroid treatment.

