## 7.1 ENDPOINT AND RESPONSE CRITERIA

### 7.1.1 Definitions

Evaluable for response: Safety, tolerability, and efficacy of AAT will be assessed from the initiation of the first AAT treatment

Complete Response (CR): All evaluable organs (skin, liver, GI tract) stage 0. For a response to be scored as CR on day 28, the patient must be in CR on that day and have had no intervening additional GVHD therapy.

Partial Response (PR): An improvement in one or more organ involved with GVHD symptoms without worsening in others. For a response to be scored as PR on day 28, the patient must be in PR on that day and have had no intervening additional GVHD therapy.

No response (NR): All responses that are not CR or PR. Patients who receive any systemic GVHD therapy other than the continuation or modification of GVHD prophylaxis, systemic steroids, and topical/non-absorbable oral steroid therapy, will be scored as NR on day 28 regardless of organ staging.

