#### **7.1.3 Steroid refractory GVHD**

Patients who are scored as no response on day 28 of systemic steroid treatment for GVHD **or** who receive additional systemic immunosuppression prior to day 28 (i.e., no response) will be considered steroid refractory. Escalation of steroid doses during treatment for GVHD are not considered in the definition of steroid refractory GVHD.

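### Section 11.3 counts any death as a primary-endpoint failure, while the endpoint, the 28% benchmark and the 6-or-fewer go rule are all set for steroid-refractory GVHD alone

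*Combined protocol and SAP*

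**What the plan says.** Section 11.3 sets out what fails the primary endpoint in a sentence that opens "Death, lack of GVHD response to systemic steroids by day 28 of treatment, or initiation of additional systemic immunosuppressive therapy for GVHD will be considered". Its next sentence reads "The incidence of steroid-refractory GVHD by day 100 in the study patients will be compared to the historical control rate of 28" percent.

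The other places that fix the endpoint, the benchmark or the decision do not name death:

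- Section 2.3: "GVHD is defined as steroid refractory if CR or PR is not achieved by day 28 of systemic steroid treatment", or if further immunosuppression was given for GVHD before 28 days of steroids.
- Section 7.1.3 uses the same two routes, starting from "Patients who are scored as no response on day 28 of systemic steroid treatment for GVHD".
- Section 11.1: "The primary study measure of efficacy is the incidence of steroid-refractory GVHD by Day 100 after HCT".
- Section 1.2, on the benchmark: "The cumulative incidence of SR GVHD by day 100 in patients who are HR at either Day 7 or 14 is 28" percent.
- Section 11.2, repeated in the synopsis: "If we observe 6 or fewer cases of SR GVHD, we will consider this approach sufficiently promising to warrant further study".

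The only competing-risk statement, in 11.3, concerns non-relapse mortality with relapse as the competing event. No section says how death before SR GVHD is handled for the primary endpoint.

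**The concern.** Read literally, 11.3 turns the endpoint into a composite of SR GVHD or death, while the benchmark, the 15% target, the cut-off and the power all remain those of SR GVHD alone. A death from relapse, infection or toxicity in a patient with no GVHD, or with GVHD that responded to steroids, would count against AAT in the trial but has no counterpart in an SR GVHD incidence of 28%.

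This is the trial's only efficacy go/no-go decision. If the 11.3 count is used, the comparison is biased against AAT and the stated 85% power is lost. If the 11.2 count is used, the design stands and the sentence in 11.3 is wrong. With both in the text, the numerator of an open-label trial could be settled after the deaths are known.

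**Working it through.** **Inputs.** From 11.2: n = 30, historical rate 28%, target rate 15%, one-sided exact test, target level 0.23, go if 6 or fewer cases. One quantity is missing from the documents: d, the proportion who die by day 100 without SR GVHD. It is an assumption here, taken as the same whether the SR GVHD rate is 28% or 15%.

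**1. The plan's own figures.** With X the number of SR GVHD cases, X ~ Bin(30, p):

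- Power: P(X ≤ 6 | p = 0.15) = 0.847, stated as 85%.
- Level: P(X ≤ 6 | p = 0.28) = 0.224, within the 0.23 target. A cut-off of 7 would give 0.368, so 6 is the largest allowed.

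The design therefore reproduces for SR GVHD without deaths.

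**2. One data set, two answers.** Take 6 SR GVHD cases and 1 death without SR GVHD.

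- 11.2 count: 6 cases, exact p = P(X ≤ 6 | 0.28) = 0.224. Go.
- 11.3 count: 6 + 1 = 7 failures, exact p = P(X ≤ 7 | 0.28) = 0.368. This is above 0.23 and above the cut-off. No-go.

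With 5 SR GVHD cases, two such deaths do the same.

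**3. Operating characteristics if the 11.3 count is used with 28% and 6 of 30 unchanged.** The failure rate becomes p + d. Power is P(X ≤ 6 | 0.15 + d) and the level is P(X ≤ 6 | 0.28 + d). At a true SR GVHD rate of 15%, the probability that the SR GVHD count is 6 or fewer while SR GVHD plus deaths is 7 or more equals 0.847 minus the new power, because a patient set with 6 or fewer failures always has 6 or fewer SR GVHD cases. The chance of at least one such death is 1 − (1 − d)^30.

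| d (assumed) | Failure rates (null, target) | Level | Power | Counts disagree, true SR rate 15% | At least one such death in 30 |
|---|---|---|---|---|---|
| 0 | 28%, 15% | 0.224 | 0.847 | 0 | 0 |
| 1% | 29%, 16% | 0.19 | 0.81 | 0.04 | 0.26 |
| 2% | 30%, 17% | 0.16 | 0.76 | 0.09 | 0.45 |
| 3% | 31%, 18% | 0.13 | 0.71 | 0.14 | 0.60 |
| 5% | 33%, 20% | 0.09 | 0.61 | 0.24 | 0.79 |

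At d = 10% (38% and 25%) the level is 0.03, power is 0.35, and the two counts disagree half the time (0.50).

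**4. Are such deaths plausible?** Section 1.2 reports 26% to 28% non-relapse mortality in high-risk patients and 19% dying from GVHD, a gap of 7 to 9 points before any relapse deaths. The 26% is a 6-month figure and the patient sets may differ, so this shows that d is unlikely to be zero but does not estimate it at day 100.

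**5. If the composite were made primary and recalibrated.** Keep the 13-point difference and take the largest cut-off with level at most 0.23:

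- d = 5% (33% vs 20%), n = 30: 7 or fewer, level 0.177, power 0.761.
- d = 10% (38% vs 25%), n = 30: 8 or fewer, level 0.137, power 0.674.
- To regain about 85%: at d = 5%, n = 39 with 10 or fewer (level 0.212, power 0.859). At d = 10%, n = 39 with 12 or fewer (0.224, 0.846) or n = 42 with 13 or fewer (0.219, 0.857).

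Exact power does not rise smoothly with n (at d = 5%, n = 40 gives 0.839), so these sizes are a guide.

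**The case against.** The best defence is that 11.3 means something narrower. The other two items in its list apply only to patients under treatment for GVHD, so death may mean death during the first 28 days of steroids. Section 7.1.1 defines no response as "All responses that are not CR or PR", so such a patient would arguably be SR GVHD already under 7.1.3, and 11.2 and 11.3 would give the same count. The sentences on either side of the list also name SR GVHD incidence, 11.3 has no cut-off of its own, and the one numeric rule appears twice, both times for SR GVHD. Finally, counting deaths makes the rule stricter, in a pilot that accepts a level of 0.23.

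Parts of this stand. The narrow reading is possible, the direction is conservative, and the no-go arises from applying the 11.2 cut-off or test to the 11.3 count. But 11.3 does not state the restriction, and under it the word death would add almost nothing to 7.1.1. Nor does the lack of a separate cut-off help: 7 of 30 against 28% fails the only test and the only cut-off in the plan. It is also true that either endpoint can be defended; what cannot be defended is a composite count set against an SR GVHD benchmark.

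**Conclusion.** The concern holds and must be fixed. As written, 11.3 conflicts with 1.2, 2.3, 7.1.3, 11.1 and 11.2 on what counts in the sole efficacy decision, and one death without SR GVHD is enough to turn a go into a no-go.

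The documents settle the existence of the conflict and the 6-versus-7 example without any assumption. The size of the power loss depends on d: from 0.847 to between 0.81 and 0.61 for d from 1% to 5%, assuming d does not depend on treatment. False-go risk is not inflated; it falls from 0.224 to between 0.19 and 0.09. If the 11.2 count governs, nothing in the design changes. How the 28% scored a patient who died during steroid treatment remains unknown from the documents.

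**What to change.** Preferred: keep SR GVHD as the primary endpoint and amend 11.3 to say that

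- the endpoint is scored exactly as in 2.3, 7.1.3 and 11.1, and this is the count used in the 6-or-fewer rule;
- death without SR GVHD is a competing event and not a case;
- death within the first 28 days of systemic steroids either does or does not count as non-response, with confirmation that the 28% was scored the same way;
- SR GVHD or death by day 100 is reported beside the primary result as a named sensitivity analysis, because otherwise an early death could only help the primary result.

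The cost is two or three sentences and a check of how the historical rate was derived. No patients are added, and power and level stay as planned. Early deaths remain visible in the sensitivity analysis, overall survival and non-relapse mortality.

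Alternative: if the sponsor wants SR GVHD or death as primary, re-tabulate the benchmark and target from the same MAGIC high-risk patients, reset the cut-off and restate the power. The cost is that re-tabulation plus either lower power at n = 30 (about 76% at d = 5%, 67% at d = 10%) or roughly 39 to 42 patients to keep about 85%.

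### Section 11.3 counts deaths and later second-line therapy as primary-endpoint failures; 2.3, 11.1 and 7.1.3 do not, and the 28% benchmark and cut of 6 are stated for SR GVHD alone

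*Combined protocol and SAP*

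**What the plan says.** **Narrow definition.** Section 2.3, repeated in 11.1, states: "GVHD is defined as steroid refractory if CR or PR is not achieved by day 28 of systemic steroid treatment", or if further immunosuppression for GVHD was given before 28 days of steroids. Section 7.1.3 matches this in substance. It counts "Patients who are scored as no response on day 28 of systemic steroid treatment for GVHD" and those "who receive additional systemic immunosuppression prior to day 28". None of the three sections lists death.

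**Broad definition.** Section 11.3 names the same primary endpoint, incidence by day 100. Its failures are death (no cause or GVHD status specified), lack of response by day 28 of treatment, "or initiation of additional systemic immunosuppressive therapy for GVHD will be considered failures". The therapy limb has no 28-day limit.

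**Related statements.** Section 7.1.5 treats any systemic agent added to steroids for acute GVHD as failure to respond to steroids. Section 5.1.7 calls second-line treatment a treatment failure. Neither carries the 28-day limit, and neither mentions death.

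**Benchmark and rule.** Section 1.2: "The cumulative incidence of SR GVHD by day 100 in patients who are HR at either Day 7 or 14 is 28" per cent. Section 11.2 uses the same rate as the null, takes an alternative of 15%, and declares the approach promising if 6 or fewer cases of SR GVHD are seen in 30 patients. Section 11.3 compares the trial result with that 28%. No section says which definition takes precedence.

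**The concern.** The go/no-go decision is a count of patients against a fixed cut, so the case definition is part of the test. Two kinds of patient change status between sections:

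- a patient who dies before day 100 without SR GVHD;
- a patient in CR or PR on day 28 of steroids who starts second-line systemic therapy later, but before day 100.

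Both are failures in 11.3 and non-cases in 2.3, 11.1 and 7.1.3. If the trial is scored by 11.3 and the 28% counts SR GVHD alone, the trial count includes events that the benchmark does not. That works against the drug. In an open-label, single-arm trial, an unsettled definition also leaves room to choose one after the outcomes are known.

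**Working it through.** **Inputs.** n = 30, null 28%, alternative 15%, go if 6 or fewer cases, one-sided exact test, target alpha 0.23, power 85% (all Section 11.2). Median GVHD onset is about one month after transplant (1.1). In high-risk patients, six-month NRM is 26% in the multicenter set and deaths from GVHD are 19% (1.2).

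**1. Reproduce the design.** P(go | p) = P(X ≤ 6), X ~ Binomial(30, p).

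- p = 0.28: 0.2238 (attained alpha)
- p = 0.15: 0.8474 (power)

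A cut of 5 gives alpha 0.1161 and a cut of 7 gives 0.3676, so 6 is the largest cut under the 0.23 target. The plan's figures reproduce, with one case definition applied throughout.

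**2. Is there room for the definitions to differ before day 100?** With onset near day 30 and steroids started then, day 28 of steroids falls near day 30 + 28 = 58 after transplant. That leaves 100 − 58 = 42 days, about six weeks, in which later second-line therapy counts only under 11.3. Death without SR GVHD can occur at any time up to day 100.

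**3. How close is the decision to one patient?** P(X = 6) is 0.137 at 15% and 0.108 at 28%. In those trials one reclassified patient reverses the result.

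**4. Effect of a broader count.** Let 11.3 add *a* to the case rate while the 28% benchmark and the cut of 6 stay fixed. Then power = P(X ≤ 6 | 0.15 + *a*) and alpha = P(X ≤ 6 | 0.28 + *a*). The values of *a* are assumptions.

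| *a* | Power | Alpha |
|---|---|---|
| 0 | 0.847 | 0.224 |
| 0.02 | 0.761 | 0.160 |
| 0.05 | 0.607 | 0.090 |
| 0.07 | 0.499 | 0.059 |

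The 7-point row takes its scale from 26% − 19% = 7 points of non-GVHD death. This is indicative only: the two figures may have different bases, and the NRM figure runs to six months rather than day 100.

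**5. How often would the two definitions give different decisions?** Suppose each narrow non-case independently has probability *q* of counting only under 11.3. The decision flips when the narrow count x is at most 6 and at least 7 − x of the other 30 − x patients are added. With *q* = 2%, 5% or 7%, the decisions differ in 7.2%, 20.0% or 29.2% of trials at a narrow rate of 15%, and in 4.8%, 10.5% or 13.5% at 28%.

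**The case against.** The best defence is that the plan has one intended definition and 11.3 is loosely drafted. The cut in 11.2 counts cases of SR GVHD, a term defined just before it in 11.1, so 11.3 need not be read as overriding it. This is also a pilot with a deliberately lenient alpha. The first part stands to this extent: nothing makes 11.3 the section that governs the test, and a reader who infers that goes beyond the text. But nothing makes 11.1 govern either. Section 11.3 explicitly lists failures for this endpoint, and 7.1.5 and 5.1.7 also omit the 28-day limit. A lenient alpha does not help, because the stated error rates still presuppose one definition.

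Other stronger readings also fail:

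- **A third, rival definition.** Sections 2.3, 11.1 and 11.3 say response *by* day 28, while 7.1.3 says *on* day 28. A reader might infer that a response gained early and lost by day 28 makes a non-case, which would raise the false-go rate. Section 7.1.1 requires the response to be present on day 28, 7.1.2 scores day-28 status against staging at steroid start, and secondary endpoint 5 repeats the day-28 rule for PR. This is a wording matter.
- **An open-ended therapy limb.** The 11.3 endpoint is incidence by day 100, which bounds it.
- **An inflated false-positive rate.** If 11.3 adds failures against a fixed 28%, alpha falls. The cost is in power.
- **A sample-size error.** The binomial arithmetic is correct.

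**Conclusion.** The concern holds: the plan is wrong as written. This is a conflict between rules and not merely missing detail, because following 11.3 literally can give a different count from following 2.3, 11.1 and 7.1.3. Death is the clearest difference; therapy added between day 28 of steroids and day 100 is the second.

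The direction, if the trial is scored by 11.3 and the 28% is SR GVHD alone, is toward not promising. The size cannot be derived from the documents, which give neither the rate of late second-line therapy nor the rate of death without SR GVHD by day 100. Across the assumed 2 to 7 points, power drops from 0.85 to between 0.76 and 0.50. The definition can move the decision; it would be too strong to say that it will. Section 1.2 does not say how the 28% was scored beyond calling it a cumulative incidence of SR GVHD. If it was in fact scored as in 11.3, the mismatch with the null disappears, but the conflict between sections remains.

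**What to change.** 1. Put one case definition in 2.3, 7.1.3, 11.1 and 11.3. It should state response status *on* day 28 of systemic steroids (changing *by* to *on*, to match 7.1.1 to 7.1.3), one window for added systemic therapy, and an explicit rule for death before day 100. The death rule should cover cause, death without GVHD, and death during the first 28 days of steroids. Simply copying 7.1.3 into 11.3 would remove death from the endpoint without anyone having decided to do so.
2. State that the second-line wording in 7.1.5 and 5.1.7 does not define the primary endpoint, or align it with the definition.
3. Confirm that the 28% was scored by the same definition, or rescore the MAGIC cohort. Then recheck the 15% and the cut of 6. For scale, if both rates rose by 7 points (35% against 22%), a cut of 8 would give alpha 0.225 and power 0.80.
4. If death or later second-line therapy is left out of the definition, report it separately.

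The cost is wording in several sections and possibly a rescoring of the historical cohort. The 28% may shift slightly. The changes should be settled before outcomes are reviewed.
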